Aim 2. Examine how diminished attention regulation impacts the WL-SPT response in FAPD. Regional brain activations after the WL-SPT (*H2a*) and functional connectivity between AMY-PFC (**H2b**) will be enhanced during a cognitive task, which will be related to higher pain ratings and response time (**H2c**).

3. Background

Functional abdominal pain disorders (FAPD) are a set of common pediatric chronic pain conditions associated with significant disability and substantial medical costs. FAPD is characterized by abdominal pain or discomfort which occurs at least for 2 months or longer in the absence of an identifiable organic cause (1). FAPD is present in 14% of youth in primary care (2), and accounts for nearly 50% of GI visits (3, 4). FAPD is associated with increased functional disability (5, 6), anxiety (7-9), and depression (10) that may persist (11, 12). Early and effective intervention is critical for preventing long-term problems; however, many (~40%) fail to respond to currently available evidence-based treatments such as cognitive behavioral therapy (CBT) (13).

Clinical anxiety is highly prevalent in FAPD and is predictive of poor outcomes. A large portion of youth with FAPD meet criteria for anxiety disorders (8, 10, 14). Anxiety exacerbates the severity of FAPD, predicts persistent pain and disability, and corresponds to poorer treatment outcomes (15-20). The PI (see *Preliminary Findings*) found that anxiety attenuates response to CBT for pain in youth with chronic pain, including FAPD (21). Although anxiety plays a key role in predicting poor FAPD outcomes, a mechanistic understanding how youth with FAPD may be cognitively impacted by their pain (22) is required to refine and modify improve upon current treatments.

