8.B. Data Management: All data will be identified with ID numbers exclusively and kept in locked files in a space in [name] research laboratory that is designated specifically for the purposes of this project. All deidentified data (with the exception of fMRI data that will be stored on a separate, secure server) will be entered into a Redcap database on a network devoted solely to the research activities of BMCP. Electronic data stored on CCHMC's network is backed up nightly. The server is maintained and all backups are conducted by the Division of Information Services. Access to data and participant identities will be limited to [name] and key study personnel (e.g., mentoring team, research coordinator, fellow). The fMRI data will also be stored on a secure server, backed up nightly, which will only be accessible to study staff.

9. Methods:

9.A. Study Design: Youth with FAPD and healthy controls will be recruited (see recruitment sections and participant inclusion/exclusion criteria below)

Pilot testing phase: To determine initial feasibility, up to 5 HC and 5 youth with FAPD who otherwise would not meet the broader fMRI safety criteria (e.g., agoraphobia, braces) will be recruited. For these participants, the cognitive task with and without WL-SPT will be conducted outside of the scanner. Measures of pain intensity, pain unpleasantness, and state anxiety will be obtained throughout. We will compare differences in RT in youth with and without FAPD after the WL-SPT. The total time of this visit is expected to be 1.5 hours.

Active study phase: At the neuroimaging visit, all children will receive an fMRI scan, where they will complete some preliminary scans and then a cognitive task, and then be removed

from the scanner to complete a water loading symptom provocation task (WL-SPT), a non-invasive validated procedure in pediatric FAPD populations to induce abdominal sensations similar to those experienced during an FAPD episode (see Walker et al., 2006). After the WL-SPT task, they will resume the fMRI scan and will complete additional scans including the cognitive task they completed earlier to assess for diminished attentional regulation. Measures of pain intensity, pain unpleasantness, and state anxiety will be obtained throughout. The duration of the brain imaging visit is two hours, with the majority of that time spent in the scanner.

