For both youth with FAPD and those that are HC, written consent from the primary caregiver and written assent from the child will be obtained. All participants will be notified that screening is necessary and study entry is not guaranteed at this point. If the child is not eligible and the family is interested in the child receiving mental health services, contact information for the psychology service at CCHMC will be provided. Following informed consent and child assent, the following screening measures will be completed with the child by a member of the research staff: a measure of FAPD symptoms/diagnosis, clinical anxiety, and questions regarding fMRI eligibility. This process takes ~10 minutes. Study staff will complete the ROME IV FAPD diagnostic checklist with the participant's gastroenterology provider to ensure that the child meets FAPD criteria. Some patients will have already completed the SCARED at their medical visit as a part of clinical practice. For those patients, SCARED data will be obtained through EPIC. The participants and families will answer questions to ensure the child can safely enter the scanner and undergo fMRI and study procedures. Screening may take place after the clinic visit. If youth are determined to be eligible, they will be invited to participate in an fMRI visit.

9.C.2. Assessments: Qualifying participants and their respective caregivers will be scheduled to complete an in-person neuroimaging visit. Next, participants will enter the MRI and perform a

cognitive task to enhance attention to pain. *Performance is measured by reaction time.* This task was previously used in brain imaging studies of healthy adults to understand the effects of pain induction, and captures a “pain-attentive” group (i.e., reaction times >100 ms) (38) thought to categorize chronic pain conditions such as FAPD. This task involves judgements on groups of digits to indicate 1) the most frequently listed digit ignoring the value, and 2) the largest digit ignoring the frequency. Similar tasks were used in a pain study of healthy adults (50), and with healthy children (without pain) with evidence of brain activations in expected areas (56).

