9.E. Data Analysis: For the fMRI data, image processing and data analysis will be accomplished using FSL (70). Each subject’s functional images will be registered to their structural data using a six-parameter linear 3-D transformation and then nonlinearly warped to standard space (MNI152) (71-73). The aCompCor approach will be used to preprocess BOLD data for functional connectivity and psychophysiological interaction analyses (74). This process minimizes the impact of global signal changes as well as signal changes induced by movement and other sources of noise. Analyses of data will be accomplished via mixed effects ANOVAs. Pain-related activation will be identified in images by comparing pre vs. post water loading data within subjects. These findings will then be contrasted across FAPD and HC groups. Multiple regression analyses will be used to examine if the changes in brain regions are related to the pain intensity/unpleasantness/anxiety. Next, changes in pain-related brain activation and functional connectivity *during* the cognitive task following the WL-SPT will be examined. There will also be a wealth of data available for exploratory analysis. Such analyses may include examining resting state FAPD data vs. HC data and exploring groups by anxiety level.

9.F. Sample Size: Analyses were powered to address pain intensity/unpleasantness differences measured during the pilot WL-SPT study (67). A Monte Carlo simulation was performed to obtain a power estimate for the analyses under the following assumptions: 1) equivalent sample sizes for the two groups, 2) covariates (age, gender, ethnicity, SES, baseline pain) will explain ($R^2 = 0.35$) 35% of the variance, and 3) an effect size difference between FAPD and HC of $d = 0.73$ is observed. Monte Carlo simulation results showed power >0.80 to detect a $d = 0.55$ difference if 20 per group (total $N = 40$) are available for analysis after proper handling of missing data. Additional power calculations using

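### Does the plan need a written response-time analysis, with a fixed response-time measure, before H2c can be tested?

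*Combined protocol and SAP*

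**What the plan says.** H2c in section 2.A ties two imaging predictions to behaviour. Regional activation and amygdala-prefrontal (AMY-PFC) connectivity after the water load symptom provocation task (WL-SPT) "will be enhanced during a cognitive task, which will be related to higher pain ratings and response time". Section 9.C.2 makes RT the task outcome: "Performance is measured by reaction time". It also describes how earlier work with the task picked out a pain-attentive "group (i.e., reaction times >100 ms) (38) thought to categorize chronic pain conditions such as FAPD", without saying what the 100 ms is measured against or whether this study will use it.

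Under section 9.A, each child in the active phase does the task before water loading. After it, the child returns for "additional scans including the cognitive task they completed earlier to assess for diminished attentional regulation". Two RT runs per child are therefore available, in youth with functional abdominal pain disorders (FAPD) and in healthy controls (HC).

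Section 9.E gives this regression: "Multiple regression analyses will be used to examine if the changes in brain regions are related to the pain intensity/unpleasantness/anxiety". The next sentence takes up Aim 2 and says that activation and connectivity during the task after the WL-SPT will be examined. RT appears in neither sentence. Section 9.F opens with "Analyses were powered to address pain intensity/unpleasantness differences measured during the pilot WL-SPT study" and adds a second calculation for imaging group differences; RT is in neither.

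The one RT comparison on paper is for the pilot in section 9.A: "We will compare differences in RT in youth with and without FAPD after the WL-SPT". That pilot enrols "up to 5 HC and 5 youth with FAPD who otherwise would not meet the broader fMRI safety criteria", is done outside the scanner, and is there to establish feasibility.

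**The concern.** A numbered hypothesis names a variable, the assessments section makes that variable the measure of performance, and the analysis section leaves it out. A reader would ask how that half of H2c is to be tested. The pilot comparison cannot do it, because there are no brain data.

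The definition of RT is also open. Three measures can be made from the planned data: post-water RT as it stands, post-water RT adjusted for the no-water run, and the change between runs. They answer slightly different questions. Raw post-water RT mixes a child's usual speed, across ages 11 to 16, with any slowing due to pain. If the measure were chosen after looking at the results, the nominal error rate for H2c would not hold. The 100 ms figure adds to the doubt, since an absolute RT and a slowing of that size would select very different children.

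**Working it through.** **What there is to reproduce.** The documents give no RT effect size, SD, test or power, so there is no RT figure of the plan's own to check. The power statement in 9.F concerns pain ratings and is not evidence here.

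**Inputs.** From the documents: 20 per group available for analysis (9.F), alpha 0.05 (9.F, imaging calculation; taken here as two-sided), two task runs per child (9.A). Assumed, because the documents give no value: correlation r between no-water and post-water RT of 0.3, 0.5 or 0.8; one brain summary measure; a true correlation of 0.58 between brain change and RT, which a test in 20 FAPD children detects with about 80% power. The Fisher approximation gives nearly the same value: tanh((1.960 + 0.842)/sqrt(20 - 3)) = tanh(0.680) = 0.59.

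**Does the choice of RT measure have a clear winner for H2c?** Let post = r × pre + e. The answer depends on which RT component the brain change is assumed to follow. Simulated power at r = 0.3 / 0.5 / 0.8:

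| Brain change correlates 0.58 with | Adjusted RT | Measure that matches the model |
|---|---|---|
| e, the part of post-water RT not explained by the no-water run | 78 / 78 / 78% | adjusted is the match |
| change in RT | 61 / 67 / 74% | change: 80 / 80 / 80% |
| post-water RT | 74 / 67 / 40% | raw: 80 / 80 / 80% |

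In the first row, raw RT has 75 / 65 / 33% and change has 57 / 65 / 75%. That row alone would make adjustment look best, but only because the model places the signal in e. The documents favour none of the three rows.

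**Is adjustment safe for comparing FAPD with HC?** Suppose the groups differ by a stable 0.5 SD in RT at both runs, with no differential slowing. The adjusted difference then estimates 0.5 × (1 - r) = 0.35 / 0.25 / 0.10 SD instead of zero. With 20 per group, adjusted RT rejects in about 19 / 14 / 8% of studies, against 5% for change. Raw RT rejects in about 34%. Adjustment has the better precision: the detectable difference at 80% power is 0.909 × sqrt(1 - r²) = 0.87 / 0.79 / 0.55 SD, against 0.909 × sqrt(2(1 - r)) = 1.08 / 0.91 / 0.58 SD for change. So precision is traded against bias.

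**What does picking afterwards cost?** With no true association, at least one of the three measures reaches p < 0.05 in 9.4 / 9.7 / 10.4% of studies. This holds for one brain measure and requires that all three be tried and the best reported.

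**The 100 ms figure.** Read as absolute RT with an assumed mean of 500 to 1000 ms and SD of 100 to 200 ms, the least inclusive case is z = (100 - 500)/200 = -2, so 98% to 100% of children exceed it. Read as slowing with an assumed mean of 0 to 50 ms and SD of 50 to 150 ms, the range runs from z = (100 - 0)/50 = 2 (2%) to z = (100 - 50)/150 = 0.33 (37%). The first reading would select almost everyone, so it could not define a subgroup. No analysis in 9.E uses the cut-off.

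**The text of 9.E read in order.** The regression sentence comes before the Aim 2 sentence, so strictly it belongs to Aim 1. On that reading the pain-rating half of H2c has no regression of its own either. The section is brief about Aim 2 as a whole, and RT is not singled out.

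**The case for a change.** The best case for a change is that H2c is a stated hypothesis and not one of the exploratory analyses that 9.E lists separately. The general line on mixed effects ANOVAs names no RT outcome, and an association between brain and behaviour is not an ANOVA contrast. One sentence in 9.E would close the gap, with no new data and at most one degree of freedom. Without it the RT measure could be selected by its result.

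Much of this stands. RT is absent from 9.E and 9.F, the pilot cannot stand in for H2c, and the RT definition affects power.

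The rest is weaker. The 9-10% error rate depends on picking after the fact, and 5% is not an established starting point: H2c already crosses several regions and connectivity with pain ratings and RT, and 9.E sets no multiplicity rule. The specific remedy of adjusted RT wins only under the model built for it, and in non-randomised groups it carries a bias that change does not. The pilot sentence does not commit the study to raw post-water RT, since it follows directly on a description of the task with and without water loading and can mean the within-child difference. A correlational sub-hypothesis does not need its own power calculation.

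**Conclusion.** The omission is confirmed on the text, but it is a gap in detail and not an error. Nothing written in the plan would produce a wrong RT result. The hypothesis names the outcome, the design supplies both runs for every child, and 9.E gives the form of model; an analyst would extend that regression to RT and use the no-water run. Whether to use it through change or through adjustment is a fair judgement. For H2c, adjusted RT has anywhere from 40% to 78% power across the three assumed models. For the group comparison it rejects falsely in about 8% to 19% under a stable 0.5 SD difference in baseline speed, against 5% for change. The 100 ms wording describes earlier use of the task and enters no planned analysis.

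These figures rest on assumed correlations of 0.3 to 0.8 between runs, one brain measure and 20 children per group. The conclusion that no single RT measure is shown to be right does not depend on their exact values. The group contrasts in pain and imaging are untouched. No change to the plan is needed.

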1. Abstract: The goal of the current project is to enhance understanding of the neural mechanisms associated with the pain experience in youth with functional abdominal pain disorders (FAPD), which is the most common and debilitating presentation of FAPD. This study will examine the neural mechanisms associated with pain induction and diminished attentional regulation during pain in FAPD. Findings from pilot studies indicate that increased anxiety in FAPD is associated with higher pain-related impairment, and that anxiety may adversely impact response to a cognitive behavioral intervention for pain. While pain outcomes improve when anxiety is also addressed in treatment for FAPD, a sizable portion fail to respond to currently available interventions. Further, the PI found that induced pain in FAPD is associated with changes in regional brain activity and functional connectivity between brain regions that are implicated in chronic pain. It is crucial to better understand the neural mechanisms which may place youth with FAPD at risk for poorer outcomes in order to ultimately develop more effective treatments. In this study, neural mechanisms of response to a pain symptom provocation task in youth with FAPD will be compared to healthy controls. The impact of anxiety levels will also be explored. This study will also examine neural mechanisms associated with disrupted attentional regulation during pain induction in youth with FAPD.

2. Purpose of Study: The *objectives* of this study are to identify neural mechanisms of increased pain in pediatric FAPD and examine mechanisms of disrupted attention in the presence of induced pain. The *overarching goal* is to determine whether youth with FAPD process pain differently than healthy youth and to identify the brain areas involved.

2.A. Specific Aims:

Aim 1. Identify neural mechanisms during pain induction using the water load symptom provocation task (WL-SPT) in youth with FAPD vs HC. **H1a.** Brain regions associated with attentional, affective, and visceral afferent processing will show greater activations after the WL-SPT in youth with FAPD vs HC. **H1b.** AMY-PFC functional connectivity will be enhanced following WL-SPT in the FAPD group vs HC. **H1c.** Increased brain activity and functional connectivity will correspond to higher pain in FAPD.

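### Does Aim 2 lack a healthy-control contrast and a reaction-time analysis?

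*Combined protocol and SAP*

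**What the plan says.** Section 2 gives the overarching goal as being to "determine whether youth with FAPD process pain differently than healthy youth". In section 2.A, Aim 1 names its comparator; H1b, for example, predicts that AMY-PFC "functional connectivity will be enhanced following WL-SPT in the FAPD group vs HC". Aim 2 is framed within FAPD, and H2a to H2c name no comparator. The abstract matches that framing: "This study will also examine neural mechanisms associated with disrupted attentional regulation during pain induction in youth with FAPD".

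Section 9.E sets the general model: "Analyses of data will be accomplished via mixed effects ANOVAs". It defines pain-related activation as the within-subject comparison of images before and after water loading, and adds: "These findings will then be contrasted across FAPD and HC groups". BOLD preprocessing is described as serving "functional connectivity and psychophysiological interaction analyses". On correlates: "Multiple regression analyses will be used to examine if the changes in brain regions are related to the pain intensity/unpleasantness/anxiety". Only then comes the task sentence: "changes in pain-related brain activation and functional connectivity *during* the cognitive task following the WL-SPT will be examined".

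Under section 9.A, all children in the active phase, HC included, do the task, leave the scanner for the water load, and repeat the task. The imaging protocol in 9.C.2 lists sequences with and without the task, and with and without water loading. Section 9.C.2 also makes reaction time (RT) the measure of task performance. The only RT comparison spelled out is the pilot's, in 9.A, between children with and without FAPD.

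**The concern.** There are two worries.

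The first is the comparator. The run order is fixed, and no counterbalancing or no-water repeat is described. Children leave the scanner after about 45 minutes, and section 6 itself expects fatigue, sleepiness and boredom. A pre/post change in task activation seen in FAPD children alone could therefore be a session effect that HC would show too. H2a and H2b might be declared supported for that reason, and the study's overarching question about a difference from healthy youth would go unanswered for Aim 2.

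The second is H2c. It predicts a relation with response time, yet the regressions in 9.E list only pain intensity, unpleasantness and anxiety. The pilot comparison cannot fill the gap: it covers at most 5 + 5 children outside the scanner and does not relate RT to brain change.

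**Working it through.** **What the text commits to.** The documents give no power or sample size specific to Aim 2, so there is no stated figure to reproduce. The texts have to be compared first.

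1. 9.E defines pain-related activation by the pre/post water-load comparison and sends those findings to an FAPD-versus-HC contrast. The task sentence uses the same term, now during the task.
2. The imaging protocol in 9.C.2 includes task runs both with and without water loading, so the pre/post data already contain task runs.
3. HC complete both task runs (9.A). The pilot RT comparison is between groups (9.A), and 9.F bases its imaging calculation on between-group changes.
4. No section states an FAPD-only test.
5. H2a can be read in more than one way: a pre/post change in task activation, task versus no task after water, or task x session. A task x session contrast, even within FAPD, would cancel session effects common to task and no-task data; task-specific repetition would remain.
6. H2c has two parts. The 9.E regressions cover pain ratings. Only RT is missing from the list, and RT is collected with the task.

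**Size of the false-positive risk if an FAPD-only test were run.** Inputs: n = 20 analysable (9.F) or 25 enrolled (9.B) per group; alpha 0.05, two-sided (sidedness assumed); a session shift of dz SDs of the change score (assumed, since the documents give none); no pain effect. The test is a paired t with n - 1 degrees of freedom and noncentrality dz x sqrt(n). For dz = 0.2 this is 0.2 x 4.472 = 0.894 at n = 20 and 0.2 x 5 = 1.0 at n = 25.

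| Assumed shift (SD) | FAPD-only, n = 20 | n = 25 |
|---|---|---|
| 0.1 | 0.071 | 0.077 |
| 0.2 | 0.136 | 0.161 |
| 0.3 | 0.247 | 0.302 |

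With the same shift in both groups, the group x session test stays at about 0.05 (simulated). If the shift differs between groups by 0.2 SD, that test rejects in 0.095 or 0.107 of studies, so it removes only what the groups share.

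**Cost of making group x session the primary test.** This is a two-sample t on change scores with 2n - 2 degrees of freedom and noncentrality d x sqrt(n/2). The effect of 0.73 is borrowed from the pain-rating assumption in 9.F; carrying it over to imaging is an assumption. At d = 0.73 the noncentrality is 0.73 x 3.162 = 2.308 (n = 20) or 0.73 x 3.536 = 2.581 (n = 25). For the FAPD-only test it is 0.73 x 4.472 = 3.265 or 0.73 x 5 = 3.65. No covariates are used.

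| Case (FAPD change 0.73 SD) | 20 per group | 25 per group |
|---|---|---|
| FAPD-only | 0.872 | 0.938 |
| Group x session, HC change 0 | 0.614 | 0.715 |
| HC change 0.1 (d = 0.63) | 0.493 | 0.588 |
| HC change 0.2 (d = 0.53) | 0.372 | 0.451 |
| HC change 0.3 (d = 0.43) | 0.263 | 0.319 |

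The effect detectable with 80% power is 0.91 or 0.81 SD for group x session, against 0.66 or 0.58 SD for FAPD-only. If the covariate R-squared of 0.35 in 9.F carried over, d would become 0.73 / sqrt(0.65) = 0.905 and group x session power about 0.79 or 0.88. 9.F makes that assumption for pain ratings, not for imaging change.

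**The case for a change.** The strongest case for a change is that two analyses with different estimands both fit the text, so the choice could be made after seeing the data. Aim 1 names HC and Aim 2 does not, and the task sentence opens a new step after the group contrast. If the group contrast was always meant, saying so would cost one sentence and no new data. The RT omission stands whichever reading is taken.

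Part of this stands. 9.E does not name the contrast for H2a and H2b, does not say which contrast the psychophysiological interaction analysis feeds, and does not list RT. An FAPD-only pre/post task change, if reported alone, would be confounded with run order.

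The rest does not carry. The plan never adopts the test that the false-positive figures describe. Those figures use an assumed shift and a scalar test, which does not translate directly to image-level thresholds. H2a and H2b also predict enhancement, so a session shift creates false support only if it is upward; fatigue or repetition that lowers activation would work against the hypotheses. Making group x session primary would not be a neutral clarification either. It alters an aim worded for FAPD, has no task-versus-no-task term although H2a can be read to need one, and subtracts any water-load response that HC share, since HC drink too. For H2c, a session shift common to all children does not by itself create an association between brain change and RT.

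**Conclusion.** No change to the plan follows. The missing comparator is a gap in detail that the surrounding text of 9.E largely fills: the model, the pre/post definition and the group contrast are all stated, and HC supply the task data needed. The missing RT term is of the same kind. H2c names the variable, 9.C.2 makes it the task measure, and an analyst testing H2c would add it to regressions already planned.

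The only alternative with real statistical consequences, making group x session primary and the within-FAPD change secondary, is a trade-off with no clear gain. It protects against session effects shared by both groups, at a cost in power from 0.87 to 0.61 with 20 per group, or 0.94 to 0.72 with 25, and more if HC respond as well. Those figures assume a 0.73 SD effect carried over from pain ratings to imaging, a two-sided 5% test and no covariates; the plan's own R-squared, if it applied, would reduce the loss. The false-positive rates of 7-8%, 14-16% and 25-30% hold only for an FAPD-only test with an assumed session shift of 0.1, 0.2 or 0.3 SD, and they count as false support only when the shift is upward. When Aim 2 results are read, a within-FAPD pre/post task change standing alone should be treated as confounded with run order.
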